B. Participant Selection: Adults ≥ 65 years assigned to the Obs Unit at the discretion of the treating physician will be enrolled (**n=380**). Patients may be in Obs as part of an Obs protocol (e.g., chest pain) or in response to a positive geriatric screening test. Patients with delirium or dementia will be enrolled with an LAR and patient assent. Exclusion criteria are need for inpatient care, non-English speaking, acute psychiatric issues, prisoners, unable to follow-up, or unable to consent and no LAR.

Study personnel will monitor the Obs Unit electronic tracking board (7am-11pm M-F and select weekends) to identify and recruit 380 patients (150 pre and 230 post cohorts).

C. Data Collection: A survey and chart review will be completed during the Obs stay (Table 3). Follow up phone interviews will occur at days 30 ± 3 and 90 ± 5 . In simulations with research staff, survey completion required 8-10 minutes of patient time. Patient data will be collected in REDCap, which has built in scoring tools for PROMIS measures. Chart abstraction will be done by research coordinators and will use standard methods (including training of abstractors, standardized forms, code book, etc).¹⁵

Data collection definitions:

OARS:¹⁶ (Primary Outcome) An assessment of activities of daily living (functional status) commonly used in ED studies. We will obtain 4 timepoints: Premorbid (patient report of function 1 week prior to ED visit), at the ED visit (day 0), and at days 30 and 90. A change of ≥ 3 points or death between is a significant decline.^{12,17}

HRQoL: The Patient Reported Outcomes Measurement information System (PROMIS) is endorsed by the NIH and PCORI. We will use the Global Health v1.2 (10 questions). A 3 point change is clinically meaningful.¹⁸

New services: Number of new or increased outpatient services (e.g., home health therapies, referral for community interventions, equipment).

New geriatric syndrome¹⁹ diagnoses of delirium, impaired cognition, fall risk, or elder mistreatment.

Geriatric clinic referral: Referrals to the Falls Prevention, Polypharmacy, or Geriatrics Clinic.

Pharmacist recommendations: Number of medication related problems/interactions.^{1,20}

Positive geriatric interventions: ≥ 1 of: new services, diagnoses, referrals, or pharmacist recs.

ED revisits and hospitalizations: Any ED revisits or unscheduled hospitalizations within 90 days.²¹

Patient satisfaction: interview data with themes of positive patient outcomes or satisfaction.

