Table3: Patient level data collected for Aim 2.

	Chart review	Patient interview
Day 0	
 - Demographics and zip code - Charlson Comorbidity Index - Observation protocol - Geriatric screening scores - Geriatric assessments - New geriatric syndromes - Geriatric clinic referrals - Medication recommendations - New services - Disposition and length of stay 	
 - OARS and HRQoL - Current level of care - Falls in the past month - Current home health and community resources - (subset) semi-structured interviews.
Days 30, 90	
 - Clinic referrals and follow-up - ED revisits and 	
 - OARS and HRQoL - Current level of care

	hospitalizations	
 - Falls since last contact - Home health and community resources used
--	------------------	--

Qualitative data: At least 20 patients in the post cohort will be selected for semi-structured interviews. Interviews will be led by a trained researcher coordinator. Purposeful sampling will be used to provide a mix of genders, ages, and Obs Unit dispositions. To assess patient satisfaction, (Aim 2b), a trained researcher will conduct in-person, semi-structured interviews with intervention patients. In addition to Likert-type questions, we will solicit brief descriptions of clinical exemplars of how this intervention produced a positive patient outcome. See interview guide. Maximum variation/heterogeneous purposive sampling will provide a mix of genders, ages, and observation dispositions. This interview will add an additional 20 minutes to the patient's participation time, and so we expect that some participants may decline this portion. With 230 patients in the post implementation cohort, we should have sufficient volume to get at least 20 patients to participate in the qualitative data collection.

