Analysis: Monthly summary statistics on geriatric patient visits, screening and consultation will be recorded. For **Hypotheses 1a.i and 1a.ii (Implementation)** we will calculate the proportions for screening rate and protocol fidelity with 95% CIs monthly using aggregate data. Success is predefined as a point estimate >80% for each outcome for 6 months. The Staff Implementation Surveys (both pre- and post-implementation) will be thematically analyzed using Atlas.ti (Cleverbridge, Inc, Chicago, IL) a qualitative data analysis program, and categorized within the CFIR framework. This data will be used to further the implementation process. Additional assessments of implementation will include: the number of improvement cycles, generated solutions and protocol adaptations, and Lean fidelity. Lean fidelity will be assessed as a yes/no variable at conclusion of implementation. For **Hypothesis 1b, (Sustainability)** we will compare the total mean scores (primary outcome) between the 2 years taking into account linked responses by the same nurses in both years using a mixed model. We will compare individuals' scores over time using a paired t-test or Sign Rank test.

B. Aim 2: Participant representativeness will be assessed by comparison to demographics of all ED patients. The *primary outcome* for Aim 2a is the proportion of patients in the pre and post cohort with a significant (≥ 3 point) decline in Functional Status (OARS) from day 0 to day 90. We will compare proportions with decline in the pre- and post-group using a Chi-square test (primary analysis). Also, logistic regression modeling will be used to compare the functional decline between the pre and post intervention groups univariately and while controlling for initial ED HRQoL, demographic factors (age, race, average socioeconomic status from zip code census tract), Charlson Comorbidity Index score,²³ number of services used and any other significant factors varying between the two cohorts. The total number of covariates will not exceed 12, given we estimate 122 subjects with functional decline. A similar secondary analysis will be done using the 30 day timepoint data.

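### The covariate rule for the adjusted Aim 2a model sets no time point for services and no limit to pre-intervention variables, so it permits (but does not require) adjustment for the protocol's own results

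*Combined protocol and SAP*

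**What the plan says.** Section IV.B makes an unadjusted chi-square test of the proportion declining by day 90 the primary analysis. It adds logistic models, univariate and adjusted. The adjusted model names initial ED HRQoL, age, race, area socioeconomic status and the Charlson score, then "number of services used and any other significant factors varying between the two cohorts". At most 12 covariates are allowed, given 122 expected declines. A similar analysis is planned at day 30.

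Table 3 holds three items that could supply a services count:

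- day-0 interview: "Current home health and community resources";
- day-0 chart review: new services, within the run "Geriatric assessments - New geriatric syndromes - Geriatric clinic referrals - Medication recommendations - New services";
- days 30 and 90 interview: "Home health and community resources used".

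The definitions in section III.C contain one services count, "New services: Number of new or increased outpatient services", and make it part of a composite: "Positive geriatric interventions: ≥ 1 of: new services, diagnoses, referrals, or pharmacist recs". Section III.A lists what the multidisciplinary assessments find among the secondary outcomes.

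**The concern.** The two cohorts are not randomised and are enrolled in different periods (months 3-15 and 33-56 in Table 2). The adjusted model is the only planned full-cohort analysis of the primary outcome that addresses confounding between them. For that purpose its covariates should describe patients as they were before the protocol acted on them.

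The rule does not ensure this. HRQoL is tied to the initial ED visit; services are tied to no time. The open clause selects on a difference between cohorts, which is what a working protocol produces in assessments, diagnoses, referrals, pharmacist recommendations and services. If such items enter, part of the protocol's effect may be adjusted away. Alternatively, patients may be compared at equal service counts that mean different things in the two cohorts. Either way the odds ratio stops estimating the total effect.

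**Working it through.** **1. The plan's own figure.** 122 / 12 = 10.17 events per covariate, so the cap of 12 fits a ten-events-per-covariate rule (my assumption; the plan does not state it). Six covariates are named: HRQoL, age, race, socioeconomic status, Charlson, services. That leaves 12 - 6 = 6 places for the open clause, fewer if race needs several terms. The cap limits how many covariates enter, not what kind.

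**2. Time order of the candidates.** The day-0 resource item can be pre-intervention. New services and follow-up resources come after the protocol acts. A day-0 label does not settle the order, because section III.C places the survey and chart review within the Obs stay. Five day-0 chart items (assessments, new syndromes, referrals, medication recommendations, new services) are steps or products of the protocol.

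**3. How the selection criterion behaves.** Inputs: cohorts of 150 and 230 (section III.B); a 5% Pearson chi-square test and pre-cohort rates of 10% to 50% (assumed). The probability of p < 0.05 for a yes/no item, by exact binomial enumeration, is:

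| True rise, post minus pre | Probability of p < 0.05 |
|---|---|
| 0 points | 0.049-0.052 |
| 5 points | 0.161-0.296 |
| 10 points | 0.482-0.759 |
| 15 points | 0.821-0.969 |
| 20 points | 0.971-0.999 |

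These are chances of testing significant, not of entering the model.

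**4. Effect on the odds ratio if a post-protocol services count enters.** All inputs here are assumed. Services are Poisson with pre-cohort mean 1. Decline is 40% pre and 27% post (150 × 0.40 + 230 × 0.27 ≈ 60 + 62 = 122), so the true OR = (0.27/0.73)/(0.40/0.60) = 0.555 and its log is -0.589. For the null, both cohorts have 122/380 = 32.1%. The fitted model is logit P(decline) = a + b·post + c·services, fitted to expected outcomes in 760,000 simulated patients at 150:230.

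- Mediator case: each service shifts the log-odds of decline by 0.25, 0.50 or 0.75 of -0.589.
- Frailty case: one SD of frailty shifts log services / log-odds of decline by 0.3/0.5, 0.5/0.8 or 0.5/1.0.

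| Post-cohort mean services | Mediator, true OR 0.555 | Frailty, true OR 0.555 | Frailty, true OR 1 |
|---|---|---|---|
| 1.1 | 0.56-0.57 | 0.52-0.55 | 0.97-0.99 |
| 1.25 | 0.57-0.60 | 0.50-0.54 | 0.92-0.97 |
| 1.5 | 0.59-0.66 | 0.46-0.52 | 0.85-0.94 |
| 2 | 0.64-0.81 | 0.40-0.49 | 0.73-0.88 |

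In the mediator case the effect is attenuated. In the frailty case post-cohort patients with a given count are on average less frail than pre-cohort patients with that count, which looks like benefit.

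**5. Control.** With equal service means in the two cohorts, as for a balanced count taken before the protocol acts, the null OR stays at 1.00. Under a true effect, the strongest frailty setting gives about 0.54 with equal means. That shift is non-collapsibility of the odds ratio, not bias: (0.554 - 0.543) / (0.554 - 0.524) is roughly a third of the shift seen in that setting at a mean of 1.1. The null column is free of this.

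**The case against.** The strongest reply is that the sentence lists patient characteristics, so its closing clause naturally means baseline imbalance. No screening, assessment, referral or diagnosis variable is named as a covariate, and section IV.B handles receipt of all three screens in a separate exploratory comparison. This stands to the extent that the wording is open rather than plainly wrong.

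A reader might infer that the services covariate is the follow-up item because both use the word *used*. That is the only word they share, neither resource item says *services*, and the day-0 item is an equally direct source. The text does not settle the time point.

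A reader might also take the 48-76% in step 3 as the chance that a protocol item gets into the model. It is not: an analyst must first offer the item as a candidate and then choose it within the cap.

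Finally, the larger distortions need a large rise in services. At a post-cohort mean of 1.1 the mediator case is almost unchanged, and some of the frailty shift under a true effect is non-collapsibility. Both points stand. They limit the size of the concern, but they do not supply the missing restriction.

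**Conclusion.** The point holds as a gap in the covariate rule. The plan permits adjustment for mediators or protocol results in the adjusted day-90 model and its day-30 analogue, and its selection criterion leans towards those items. The documents do not support the stronger claim that such variables will be adjusted for.

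Nor do they support a claim that the primary result is compromised: the chi-square test and the univariate model contain no covariates.

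The size and direction of any bias cannot be derived from the documents, which give no expected change in services. On the assumed inputs, a rise in mean services from 1 to 1.5 moves a true OR of 0.555 to 0.59-0.66 in the mediator case. In the frailty case it turns a true null into 0.85-0.94. With a rise to only 1.1 the null becomes 0.97-0.99. It should be fixed, because this model carries the confounding control and the remedy is a sentence or two.

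**What to change.** Amend section IV.B as follows.

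- **Services.** Define the covariate as the number of resources recorded under "Current home health and community resources" that were already in place at day 0, before any protocol-driven referral.
- **Other factors.** Limit them to patient characteristics already collected that were fixed before the protocol acted on that patient, such as falls in the past month or premorbid OARS. Preferably list them in advance, within the cap of 12.
- **Exclusions.** Keep new services, assessments received, new diagnoses, referrals, pharmacist recommendations and follow-up service use out of the main adjusted model. Label any model containing them exploratory or mediation.
- **Conditional items.** Use current level of care or observation protocol only where the value reflects status before the protocol acted. Table 3 shows no separate pre-visit level of care and no separate medical reason for placement, and section III.B says "Patients may be in Obs as part of an Obs protocol (e.g., chest pain) or in response to a positive geriatric screening test".
- **Day 30.** Apply the same rule.

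The cost is SAP wording. The services item, falls and premorbid OARS are already collected, so these need no new data and add no patient burden. That is not established for the two conditional items, which can be left out. With a list fixed in advance, an unforeseen pre-intervention imbalance would go into a labelled sensitivity model rather than the main one.

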B. Intervention: The two-step intervention will begin with the patient's primary ED nurse screening for geriatric syndromes. The ED physician will then determine if multidisciplinary intervention is needed and the appropriate level of care (eg, dementia may cause a positive delirium screen, but may not require evaluation if cognitive status is at baseline). Patients requiring multidisciplinary assessment will be either admitted or assigned to the Obs Unit for geriatric assessments based on standard care of their medical problems. These assessments are in addition to usual care for the patient's underlying medical complaint. Geriatric consultation involves evaluation by the hospital's geriatric consultation team: a board certified geriatrician, a geriatric nurse practitioner, and fellows. PT assessments are done by hospital PTs. Medication reviews are completed by ED pharmacists and include confirmation of medication list and dosages and assessment of possible medication interactions or potentially

inappropriate medications using standard criteria.¹ The case management team includes nurse case managers and licensed social workers.

This intervention is already in place, however currently only 5% of older adults in the ED are receiving the screening and only 11% are placed in the Obs Unit for further assessment. Based on data from other institutions, this is likely an underutilized service and we are missing many older adults with acute needs. The goal of implementation is to increase nurse screening to >80% and protocol compliance to >80%.

C. Rationale for study: The data collected for Aim 1 is partly from our baseline ED metrics but also data collected as a result of our accreditation as a Level 1 Geriatric ED. As part of that process, we have to track dispositions, 72 hour return rates, morbidity and mortality reports, readmissions, and geriatric screening rates. This is current monthly report. Additionally, we have to do chart reviews to assess compliance to our geriatric quality protocols. The intervention in question is included as part of our geriatric protocols. This intervention is not "new", it has been ongoing since 2015. However, a formal implementation process is needed as education and accreditation have not been able to increase our screening and compliance rates above 5%. For this reason, [name] took 80 hr of Lean Six Sigma Green Belt training in 2017-2018.

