Secondary outcomes for 2a: Dichotomous secondary outcomes will be analyzed using proportions and chi-square tests between pre- and post-intervention groups and with exploratory logistic regression models. Count data will be explored using either Poisson or negative binomial regression. *Exploratory analyses* will use similar methods to compare the pre-intervention group to the post- subgroup who received all 3 screens.

F.12.ii *For Aim 2b,* interviews will be transcribed verbatim and entered into Atlas.ti. We will conduct manifest content analysis of the descriptions using phrases and sentences as our unit of analysis.^{24,25} We will categorize the exemplars and analyze for appropriateness and perceived outcomes based on the level of detail provided. Analysis will include open and axial coding procedures using techniques of constant comparison and questioning within and across cases.^{26,27} The coding schema will be created with consensus on coding definitions and grouping codes into code families/categories. Dual coding with negotiated consensus will be performed on 20% of the data to add rigor to the analysis. Themes will be reported per current guidelines.^{28,29}

V. References

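### The exploratory comparison of the whole pre cohort with only the fully screened post patients is selected on one side, so it can be biased in either direction

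*Combined protocol and SAP*

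**What the plan says.** The primary analysis of Aim 2 (Section IV.B) is a chi-square test of the proportion with significant OARS decline from day 0 to day 90, in the full pre and post cohorts. Logistic regression is added, controlling for initial HRQoL, age, race, area socioeconomic status, Charlson index, services used and other factors that differ significantly between cohorts.

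Under the secondary outcomes for 2a, the plan adds exploratory analyses, by methods similar to the chi-square, logistic and count models just described, that "compare the pre-intervention group to the post- subgroup who received all 3 screens". No matching restriction, weighting or comparison of screened with unscreened post patients is described.

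Four other places bear on this:

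- **Section I.B** makes screening an event after arrival: "The two-step intervention will begin with the patient's primary ED nurse screening for geriatric syndromes". It also reports that "currently only 5% of older adults in the ED are receiving the screening" and sets a target above 80%.
- **Section IV.A** counts a patient as screened only if all three tools are documented, including the 4 Stage Balance Test.
- **Section III.B** gives two routes into the cohort: "Patients may be in Obs as part of an Obs protocol (e.g., chest pain) or in response to a positive geriatric screening test".
- **Table 3** lists "Geriatric screening scores" among the day-0 chart items, along with the Charlson index and the observation protocol. Section III.C adds premorbid and day-0 OARS.

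**The concern.** The two sides are not selected in the same way. Post patients without all three screens drop out of the comparison, while pre patients of the same kind stay in. The outcome is functional decline, and one of the screens is a balance test, so whether a patient is fully screened could well be related to prognosis. If it is, the comparison mixes any effect of the protocol with the difference between patients who are and are not screened.

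The chi-square test does nothing about this. The logistic model may do something, but its named covariates omit baseline OARS, cognition and mobility. The clause admitting other factors that differ between cohorts might bring some of these in, but that depends on the data and is not assured.

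What is at stake is interpretation. Screening is the first step of the intervention, so a reader could take this comparison as the effect of the protocol when delivered, particularly if the full-cohort result is null.

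**Working it through.** The plan gives no figure for this comparison, so there is none to reproduce. The check asks how far the comparison moves when the protocol has no effect at all.

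**Inputs from the documents**
- Cohorts: 150 pre and 230 post (Section III.B).
- Expected declines: 122 in total (Section IV.B), so 122/380 = 32.1%, taken as 32% in both cohorts under no effect.
- Screening target: above 80% of older ED patients (Section I.B).

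**Assumptions**
- Screened share among enrolled post patients c = 0.80, giving 0.80 × 230 = 184 patients. The target applies to all older ED patients, not to Obs Unit participants.
- Risk of decline in unscreened post patients r: 20%, 32%, 40% or 50%. The documents give no value.
- Two-sided 5% test of two proportions; no level is stated.

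**Step 1: risk in the screened subgroup.** Overall post risk must stay at 32%, so screened risk = (0.32 − 0.20 × r)/0.80.
- r = 40%: (0.32 − 0.08)/0.80 = 30.0%
- r = 50%: (0.32 − 0.10)/0.80 = 27.5%
- r = 32%: (0.32 − 0.064)/0.80 = 32.0%
- r = 20%: (0.32 − 0.04)/0.80 = 35.0%

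**Step 2: how often the test rejects, 150 v 184.** With d = 0.32 − screened risk, SE0 the pooled and SE1 the unpooled standard error:
- P(false benefit) = Φ((d − 1.96 × SE0)/SE1)
- P(false harm) = Φ((−d − 1.96 × SE0)/SE1)

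For r = 50%: d = 0.045, SE0 = 0.0502, SE1 = 0.0503. False benefit = Φ((0.045 − 0.0983)/0.0503) = 14.5%; false harm 0.2%; total 14.7%.

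| Unscreened risk | Screened risk | Spurious difference | False benefit | False harm | Total |
|---|---|---|---|---|---|
| 50% | 27.5% | 4.5 points benefit | 14.5% | 0.2% | 14.7% |
| 40% | 30.0% | 2.0 points benefit | 5.9% | 0.9% | 6.8% |
| 32% | 32.0% | none | 2.5% | 2.5% | 5.0% |
| 20% | 35.0% | 3.0 points harm | 0.5% | 8.3% | 8.8% |

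**Step 3: the same null in the full cohorts.** With 150 v 230, both at 32%, false benefit and false harm are 2.5% each. The distortion comes only from restricting one side.

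**Step 4: sensitivity to the screened share.** Now set the unscreened risk at 1.5 times the screened risk, overall 32.1%. False benefit is 16.6% with 60% screened, 8.4% with 80% and 5.0% with 90%. The problem shrinks as screening approaches completeness.

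**The case against.** The strongest reply is that the analysis is labelled exploratory, the primary test uses the full cohorts, and the distortion is small if screening meets its target and risks differ modestly. All of that stands, and it limits the point to one secondary result.

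Some stronger readings are tempting but are not supported:

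- **That the bias favours the intervention.** A reader might infer that patients too weak or confused for the balance test lose their place in the subgroup. The documents do not say how inability is recorded; it may be charted as a positive screen. Patients needing inpatient care are excluded from both cohorts, which limits how unwell the unscreened can be. A positive screen is itself a route into the Obs Unit, which could enrich the screened subgroup with frailer patients, and nurses may skip low-risk patients who are there on an Obs protocol. Either would push towards apparent harm.
- **That the inflation is very large.** With 70% screened and unscreened patients declining at 50%, the same formulas give a spurious benefit of 7.7 points and 33% rejection. That needs a screened share below the one the plan expects: the post cohort is enrolled in the Maintenance/Sustainability phase (Table 2), which follows six months above 80%. Screening could slip as support is withdrawn, but this is not the planned case.
- **That there is no adjustment at all.** Logistic models are among the similar methods, so the fair criticism is incomplete adjustment. Whether the full Aim 2 covariate list carries over is not stated.

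**Conclusion.** The concern holds in limited form. Comparing an unrestricted pre cohort with post patients selected by care after arrival can produce an apparent benefit or an apparent harm when there is neither. The documents do not determine which.

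At 80% screened, the illustrated shift runs from 4.5 points of spurious benefit to 3 points of spurious harm. These sizes rest on the assumed screened share among participants, the assumed risk in unscreened patients, and the 32% overall rate implied by the plan's own event count. If screening is unrelated to prognosis, the bias is zero.

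A reader might infer that the main Aim 2 conclusion is undermined. It is not: the full-cohort chi-square does not use screening status. The point is worth acting on because a result of unknown sign and size is hard to interpret, and the plan can be improved before analysis with data it already collects.

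**What to change.** Amend the exploratory analysis in Section IV.B as follows:

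1. Weight the pre cohort to resemble the screened post patients, or adjust in the regression, using premorbid and day-0 OARS, age, Charlson index and Obs protocol, in place of the unadjusted chi-square. Name these variables in advance.
2. Tabulate baseline characteristics and outcomes of screened and unscreened post patients, so that the direction and strength of the selection can be seen.
3. Show the result beside the full-cohort result, and state that it is not to be read as the effect of receiving the protocol.

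The cost is a few sentences in the plan and a little analysis, with no new data collection. The interval will be somewhat wider than that of the naive comparison. Only measured differences are handled: cognition and mobility may remain unbalanced, and screening scores may be sparse in the pre cohort if its screening was near the 5% reported for the ED.

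An alternative would divide the full-cohort difference by the pre–post change in the share receiving all three screens. I would leave it out, or report it only with its assumption stated: that the whole pre–post change acts through receiving all three screens. Staff training, partial screening, secular change or a shift in Obs case mix could each break that assumption.
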